 - c. *H2_c: Relative to historical matched controls drawn from previous years of the program, participants receiving sessions will demonstrate greater reductions in HIV sexual risk behavior.*
- 3) **Secondary Aim:** Estimate the effect of MoodGym on the uptake/adherence to ART and PrEP among HIV-positive and HIV-negative participants, respectively.
 - a. *H3_a: Increased attendance to sessions will be associated with lower comorbid depression scores which, in turn, will be associated with increased likelihood of ART medication uptake and/or adherence for HIV-*

positive participants as well as increased likelihood of PrEP uptake and/or adherence for HIV-negative participants.

INTRODUCTION

[figure not shown]
Background

Each year, 70% of new HIV infections in the United States occur with MSM,¹ and use is identified as a major driving force in the continued HIV/AIDS pandemic affecting MSM communities.² Though studies have consistently demonstrated associations between use and HIV transmission among MSM,^{3,4} recent research has further illustrated that depression is likely an under-recognized mechanism in the /HIV link, statistically both mediating and moderating the link between use and engagement in sexual risk behaviors.⁵ Further, depression is an obstacle to medication adherence for both HIV-positive and HIV-negative MSM; depression has been associated with reduced adherence to ART medication,^{6,7} and MSM in the iPrex study with the highest levels of depression also demonstrated the lowest levels of PrEP adherence,⁸ highlighting the important effects of depression on biobehavioral efforts to limit HIV transmission among MSM.

STUDY DESIGN

This study is a single-arm, non-randomized pilot study. Eligible participants are newly enrolled Getting Off service program participants who will be invited to participate in the study during their enrollment, and can enroll in the study at any time during their first two weeks of program participation (see Figure 1).

Figure 1: Study Design “Depression Intervention to Optimize Methamphetamine Treatment Outcomes among Gay and Bisexual Men”

Study activities will take place contemporaneously with participation in the service program (i.e., participants enroll during their first or second week of Getting Off, and

complete the 5 sessions over the remaining 6-7 weeks). If participants complete all five MoodGym modules prior to the 8-week endpoint, they will be offered the chance to revisit prior module(s); assessments and incentives will continue as scheduled. Getting Off program evaluation data from study participants will be matched and compared with historical program evaluation data to assess the impact of the MoodGym intervention on the Getting Off program outcomes through an observed treatment effects analysis.

MoodGym

MoodGym is a seven module computer-optimized, evidenced-based intervention for adults with depression and/or anxiety symptoms. Though MoodGym modules can be taken by participants without assistance, evidence suggests results may be improved by applying in a more structured setting. In this pilot study, MoodGym will be delivered with support and guidance from a trained Study Counselor. Each week participants will be asked to attend one one-hour individual appointment with the Study Counselor to complete a MoodGym module, for up to seven weeks.

Phone Call After One Missed Session of MoodGym

The SC will monitor participant attendance and conduct a phone call to any participant who does not attend a scheduled session, to reschedule.

SELECTION AND ENROLLMENT OF PARTICIPANTS

Inclusion Criteria

- A participant enrolled in the Getting Off service program at Friends Community Center; and,
- Within his first or second week in the program

Exclusion Criteria

- Not a participant in his first or second week of the Getting Off service program at Friends Community Center

STUDY PROCEDURES

Recruitment and Enrollment

Participants will be recruited from the Getting Off service program at Friends Community Center. Program participants will be invited to participate in the study at the time that they enroll in the program, and may enroll in the study at any time during their first or second week of program participation. Getting Off program staff will inform new participants about the research study. If the potential participant is interested in learning more about the study he will be directed to meet with the Study Counselor. Both the program staff and the SC will emphasize that participation in this study is voluntary and that participation in the program is not dependent on participation in this study. Interested participants will meet with the in a private room, then read the consent form, have questions answered by the, and sign the consent form if they wish to participate.

All in-person contact (recruitment, screening, consenting, MoodGym sessions, and administration of follow-up interviews) with participants will take place in a private room with a closed door at Friends Community Center. Any telephone calls made to

participants during the course of the study will be made from a private office with a closed door, so the phone conversation cannot be heard.

MoodGym Intervention

MoodGym is an Internet-based CBT program that uses fun, engaging, interactive content, alongside character-driven narratives, to help alleviate symptoms of depression and comorbid anxiety. The program also aims to improve the individual's functioning by promoting the development of skills and strategies to manage depression.

MoodGym consists of an introduction module, five structured intervention modules, and a workbook of assessments.

1. Getting Started
 - a. An introduction to MoodGym, including CBT, the different characters and structure of the intervention content, and baseline mental health quizzes (e.g., depression, anxiety) that are scored in real time to help the participant understand their current level of mental health symptoms. This will be done during the first MoodGym session, given its brevity and relationship to the first module.
2. Feelings Module
 - a. Understanding emotions, mood, and physical reactions of depression and anxiety, as well as the impact of your perspective on your personal feelings. Demonstrates links between events, thoughts, feelings, and behaviors.
3. Thoughts Module
 - a. Addresses unwelcome, unhealthy, or intrusive thoughts, and demonstrates how some thoughts can help you overcome mental health symptoms. Discusses how to improve self-esteem by changing thought patterns.
4. Unwarping Module
 - a. Introduces the idea of “warpy” thoughts, including false impressions that one must be perfect, that one can control all things, or that one is worthless if they are criticized.
5. Destressing Module
 - a. Discusses means and strategies to reduce stress, which can have important impacts on depression and anxiety symptoms, and mental health more generally.
6. Relationships Module
 - a. Discusses how relationships can both benefit or worsen one's mental health, and how to monitor and maintain healthy relationships.
7. Workbook
 - a. Contains all quizzes and tests the participant encounters during each of the above sessions. If a participant would like to retest themselves on some dimension (e.g., depression, anxiety, warpy thoughts), they can revisit the assessment in the Workbook section, and receive an updated score in real time.

Each MoodGym session will last up to one hour and will begin with the brief CESD-R assessment, administered by the Study Counselor via the same computer as the MoodGym intervention, followed by one of the five online modules, which are self-contained and guide the participant through all intervention content. Online modules include quizzes, videos, characters, interactive activities, informational content, personal stories, workbook activities, and content summaries. Sessions can also include interactions with the Study Counselor, as much or as little as the participant chooses to initiate, including supportive feedback, guidance, help, and encouragement on activities.

Incentive Schedule

All incentives will be paid in gift cards, no cash will be given. The total amount a participant can earn for participating in the study is \$70. Participants can earn \$10 for each session they attend, up to seven session, at the conclusion of each session. After each gift card is dispensed, participants will be asked to sign a sheet, specific only to them, indicating they have received the incentive payout.

Timeline

Table 1. Proposed Timeline of Study Activities

Study Activities	Month	Year 1											
		Q1			Q2			Q3			Q4		
		1	2	3	4	5	6	7	8	9	10	11	12
Obtain IRB Approval		X	X	X									
Hire/Train Study Counselor			X	X									
Enroll 42 MA-Using MSM (6/mo)					X	X	X	X	X	X	X		
MoodGym Implementation					X	X	X	X	X	X	X	X	X
Data Cleaning & Analysis													X
Begin Publication & Dissemination													X

STATISTICAL CONSIDERATIONS

Assessments

1. Center for Epidemiologic Studies Depression Scale (Revised). The Center for Epidemiologic Studies Depression Scale (Revised) [CESD-R]⁹ is a widely used depression assessment which consistently shows strong psychometric properties and concurrent validity with clinical diagnostic instruments.¹⁰ The CESD-R will be administered at the start of each session.

2. ART and PrEP Uptake and Adherence. Administered at baseline enrollment in the pilot study and 3-month follow-up only. The ART and PrEP Uptake and Adherence form briefly queries HIV-positive and HIV-negative participants as to whether they have begun and/or adhered to a prescribed ART or PrEP regimen in the past 3 months.

Statistical Analyses

Specific statistical analyses will be chosen based on the distributional properties of the variables being analyzed; sociodemographics or other variables found to significantly influence primary outcomes may be tested for inclusion as statistical controls and/or bases for contingency analyses. The outcome of primary analytical interest, i.e., engagement in HIV sexual risk behaviors, is most amenable to analyses employing the negative binomial or logistic link functions, for count and dichotomous operationalizations, respectively. Descriptive statistics will be provided for all variables, and inferential models related to Specific Aim 2 will assume three complementary but parallel analytical approaches. First (H2_a), an observed treatment effects dosage response analysis will test for observed associations between attendance to the weekly sessions and reductions in both the magnitude (negative binomial) and/or likelihood (logistic) of engagement in HIV sexual risk behaviors [note: sexual risk behavior data is gathered during standard *Getting Off* procedures]; analyses will be double-robustly estimated to ensure proper model specification.¹¹ Second (H2_b), the same model will be estimated, but will further include participants' CESD-R depression scores both as a main effect, as well as in a statistical interaction term with the number of sessions attended. Planning such a nested analysis allows for full specification of the effects of depression, both directly and in response to the intervention. Third (H2_c), participants' HIV sexual risk behavior outcomes will be statistically contrasted against those same outcomes from a group of historical matched controls sampled from the program (2009-2017) and matched using either caliper or nearest neighbor algorithm (based on method of best fit)¹² using participant age, race/ethnicity, HIV status, and the severity of their use. The proposed Secondary Aim will be tested using the Bernoulli family and logistic link function, where uptake or satisfactory (i.e., $\geq 85\%$) adherence to ART/PrEP during the course of the intervention will be coded a "1", "0" otherwise, and regressed on intervention exposure and/or CESD-R depression scores.

Missing Data

General Estimation Equation (GEE) analyses will test patterns of missing data in the follow-up assessments. Follow-up assessment data will be coded trichotomously (i.e., observed, intermittent missing, missing due to dropout) and regressed on arm assignment and relevant covariates (e.g., racial/ethnic identity, age) to ensure appropriate application of inferential logic. If a non-ignorable pattern of missing data is discovered (note: confirmed by Little's test of non-random missingness), sensitivity analyses will be conducted to ascertain which missing data management strategy (e.g., multiple partial imputation) should be applied.

DATA COLLECTION AND CONFIDENTIALITY

MoodGym Online Modules

The online modules do not report any sensitive data related to participants' mental health. All usage measures will be based on the recording of the modules completed by each participant during weekly sessions, and depression symptoms and trends are assessed via the weekly CESD-R assessments.

Study Counselor-Administered Assessments

The will briefly assess participants' depression symptoms (via the CESD-R) at the

beginning of each weekly session, and HIV-related medication uptake/adherence (via the ART and PrEP Uptake and Adherence form) at baseline and 3 month follow-up. In both cases, assessments will be administered via an online data entry form administered from the same computer the sessions are accessed. The online data entry form and short-term data hosting will be contracted using Qualtrics, a global data entry firm Friends Research Institute has ongoing multi-year contracts providing access to online survey creation and implementation software. The Qualtrics' system is HIPAA compliant and conforms to industry standard (e.g., ISO 27001 and FEDRAMP compliant) encryption and data security. Study data will be hosted on the Qualtrics cloud for the duration of the study, and will be removed at the completion of the data collection phase.

MONITORING AND ADVERSE EVENT REPORTING

Adverse event reporting will follow the WIRB policies. Serious adverse events (SAEs) include any of the following outcomes for the participant: 1) death; 2) acute life-threatening incidents; 3) hospitalization or the prolongation of a hospitalization; or 4) persistent or significant disability. SAEs events may be communicated to the principal investigator by participants or staff, or may be observed directly by the principal investigator. SAEs will be reported regardless of whether they are considered study-related.

Distress Policy

In the instance of:

- 1) a participant presenting with a gun or other weapon, and/or threatening physical violence against staff, himself, or an identified other person;
- 2) a family member or friend of a participant informing a staff member that a participant is threatening to harm staff, himself, or an identified other person;

the Friends Community Center *Distress Protocol for Participants at Friends Community Center* is automatically triggered. Staff immediately contact a trained counselor or clinician to assess the situation and advise management. Staff are provided with a phone tree providing the names and contact information (including mobile phones and pagers) for six trained counselors/clinicians familiar with, and who have agreed to carry out, the Friends Community Center *Distress Protocol*. In the case of extreme immediate threat, staff are trained to remove themselves, immediately dial 911, and to ensure the safety of themselves, other staff, and participants above all else.

Regulatory Updates

The principal investigator will report any information related to unanticipated risks or new information that may change the risk-benefit ratio to the WIRB IRB. This information may come from the current study or findings from other studies. Any changes in the protocol or consent as a result of this information will be promptly reported to the WIRB and CHIPTS. The Principal Investigator will also report any irregularities in the conduct of the study such as: participant enrollment; obtaining informed consent; and, data collection and processing.

HUMAN PARTICIPANTS

Institutional Review Board (IRB) Review and Informed Consent

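### H2_c does not require historical controls to be chosen regardless of follow-up availability, and the missing-data rule does not clearly cover the study-versus-historical contrast

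*Combined protocol and SAP*

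**What the plan says.** The Study Design section states: "This study is a single-arm, non-randomized pilot study". H2_c supplies the only comparator. The Statistical Analyses section says of the study men that their "HIV sexual risk behavior outcomes will be statistically contrasted against those same outcomes from a group of historical matched controls sampled from the program". These controls come from the years 2009-2017 and are to be matched "using participant age, race/ethnicity, HIV status, and the severity of their use". Retention and availability of a follow-up outcome are not among the matching variables. The section does not say whether a man needs a follow-up report to be eligible as a control, how men without one are treated, or at which assessment the outcome is taken. A note there adds that "sexual risk behavior data is gathered during standard" program procedures, so the outcome is program data and is not collected at MoodGym sessions.

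Study men receive $10 "for each session they attend, up to seven session" (Incentive Schedule). The Study Counselor will "conduct a phone call to any participant who does not attend a scheduled session, to reschedule" (Phone Call After One Missed Session of MoodGym). In-person study contact takes place at the program site, and incentives continue as scheduled for men who finish the modules early.

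The Missing Data section codes follow-up data as observed, intermittently missing or dropped out, and has this code "regressed on arm assignment and relevant covariates". Sensitivity analyses to choose a handling strategy follow only if a non-ignorable pattern is found, with Little's test named as the confirmation.

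**The concern.** Matching at intake makes the groups comparable when they start. It does nothing about who still has an outcome at the end. If the two groups lose different shares of men, and the lost men differ in sexual risk from those who remain, a contrast among observed men differs from the contrast among all matched men even when MoodGym has no effect.

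The plan gives a reason to expect different losses: paid, prompted visits to the site where the program collects its outcome data are described for study men only.

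The Missing Data section does not clearly address this, for four reasons.

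- *Arm* has no defined meaning in a single-arm study.
- The Assessments section lists only the CESD-R and the ART/PrEP form, so it is unclear whether *follow-up assessments* includes the program's sexual-risk data or historical records.
- Little's test assesses departure from missing completely at random. Rejection is compatible with missingness explained by measured variables, and non-rejection does not exclude non-ignorable missingness.
- Missingness that depends on measured variables can also distort an observed-case contrast, but it would not meet the stated trigger.

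Without a fixed rule, an unadjusted contrast among observed men is the likely default.

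**Working it through.** **The plan's own figures.** Table 1 gives 6 men per month with seven months marked: 6 × 7 = 42. The incentive total also agrees: $10 × 7 = $70. The plan states no power, event rate, dropout rate or matching ratio, so there is nothing further to reproduce.

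**Assumed inputs (none is in the documents).** One control per study man; no true MoodGym effect; risk among men always observed p_k = 30%; risk among men normally lost p_l = 45-65%; historical availability a_h = 50-70%; study availability a_s = 70-90%. The extra men observed in the study group are taken from those normally lost.

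**Formula.** Observed historical risk = p_k. Observed study risk = [a_h × p_k + (a_s − a_h) × p_l] / a_s. The spurious difference is therefore (1 − a_h/a_s) × (p_l − p_k).

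| a_h | a_s | p_l | Study risk observed | Historical risk observed | Spurious difference (points) |
|---|---|---|---|---|---|
| 70% | 70% | any | 30.0% | 30% | 0 |
| 70% | 80% | 45% | 31.9% | 30% | +1.9 |
| 60% | 80% | 55% | 36.25% | 30% | +6.25 |
| 50% | 90% | 65% | 45.6% | 30% | +15.6 |

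Third row in full: (0.60 × 0.30 + 0.20 × 0.55) / 0.80 = 0.29 / 0.80 = 0.3625. Over the assumed ranges the difference runs from 0 to 15.6 points. It is zero when availability is equal or when lost and retained men have the same risk.

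**Masking.** Suppose that MoodGym lowers every study man's risk by 15 points. With the third-row inputs, observed study risk is (0.60 × 0.15 + 0.20 × 0.40) / 0.80 = 21.25%. The observed difference is −8.75 points instead of −15.

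**Opposite direction.** If lost men have lower risk (30%, against 50% in men always observed), the difference favours MoodGym. At 70% versus 90% it is (1 − 0.70/0.90) × (0.30 − 0.50) = −4.4 points. At 50% versus 90% it is −8.9 points.

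**Precision, for scale (95% half-width at about 35% risk).**
- All observed, 42 versus 42: 1.96 × √(2 × 0.35 × 0.65 / 42) = 0.204, about 20 points.
- Third-row availability, 42 × 0.80 ≈ 34 versus 42 × 0.60 ≈ 25: 1.96 × √[0.35 × 0.65 × (1/34 + 1/25)] = 0.246, about 25 points.

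**Could the planned missingness regression find the gap?** Take *arm* to mean study versus historical. A two-sided 5% test of two proportions with 42 versus 42 men then has 83% power for availability of 50% versus 80%, 52% for 60% versus 80%, and 18% for 70% versus 80%. A gap that matters could easily go undetected.

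**The case against.** The strongest reply is that the mechanism is partly inferred.

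- Payments and calls attach to MoodGym sessions, while the outcome comes from program procedures common to both groups. Better outcome availability in study men is plausible but indirect. This stands, and it is why the point is that availability *may* differ.
- A reader might infer that historical outcomes exist only for men the program retained, or that historical men had no incentives or outreach. The documents say neither. They describe nothing about the program's incentives or contact in 2009-2017, do not say whether men who left were followed up, and give no follow-up rate.
- A reader might also infer that no planned analysis could reveal a difference in availability. That goes too far. The regression of missingness on arm is planned without a condition; only the sensitivity analyses are conditional. H2_c is the only two-group contrast, so study versus historical is a natural reading of *arm*. The term is still undefined, power is limited, and no handling method is fixed.
- H2_c concerns reductions, whereas the illustration compares end-point risk. If lost men also had higher risk at intake, bias in the reduction could be smaller. This is a fair limit on the size.
- In the third-row example the bias is about a quarter of the half-width, so it would rarely decide a significance test. But Specific Aim 2 is to estimate an effect, and a systematic shift in the estimate is not reflected in the interval.

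**Conclusion.** The point holds as a gap in specification. H2_c does not require controls to be selected regardless of follow-up availability. The Missing Data section does not clearly cover this contrast, and its trigger rests on a test that cannot confirm what it is asked to confirm. Under the assumed inputs the spurious difference is 0 to about 16 points, against a half-width of about 20 points with everyone observed and about 25 points with 34 versus 25 observed.

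The size rests wholly on assumed availability and risk rates and on 1:1 matching. It is zero if availability is equal in the two groups under this model. A bias against MoodGym is a tempting conclusion, but the direction is not fixed: the sign reverses if lost men have lower risk. The documents do not establish that a bias exists, only that the plan neither prevents nor reliably detects one. The change is worth making before analysis.

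**What to change.** **Statistical Analyses, H2_c.** State that historical controls are selected and matched on intake data without regard to whether a follow-up outcome exists. Name one program assessment time point and use it in both groups. Report the share of men observed at that time point in each group.

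**Missing Data.** For H2_c, define *arm* as study versus historical, and say that the section covers the program's sexual-risk data in both groups. Remove the Little's-test condition. Pre-specify multiple imputation or inverse-probability-of-observation weighting from intake variables as the H2_c analysis. With about 42 study men, use one simple model that includes group, because separate models by group would be fragile. Add a sensitivity analysis in which the risk of unobserved men may differ from that of observed men by an amount that can vary by group. It is needed because intake-based models correct only the missingness that intake variables explain.

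**Cost.** Plan wording, modest extra programming on data already held, and a somewhat wider interval. If availability turns out to be similar in the two groups, the reported shares will show that unequal follow-up was not a material problem.

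### H2_c draws controls from 2009-2017 without considering entry year, so a calendar trend in risk behaviour could mimic or mask a MoodGym effect

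*Combined protocol and SAP*

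**What the plan says.** The Study Design section describes a single-arm, non-randomized pilot, so there is no concurrent control group. The comparison with men outside the study is H2_c. The specific aims frame it as "Relative to historical matched controls drawn from previous years of the program", with the prediction that "participants receiving sessions will demonstrate greater reductions in HIV sexual risk behavior".

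The Statistical Analyses section words the test differently: "participants' HIV sexual risk behavior outcomes will be statistically contrasted against those same outcomes" in the comparison group. That group is described as "a group of historical matched controls sampled from the program (2009-2017"). Its members are to be "matched using either caliper or nearest neighbor algorithm (based on method of best fit"). The basis for the match is four characteristics: "using participant age, race/ethnicity, HIV status, and the severity of their use". No matching ratio is given. Entry year is not listed, and no restriction to recent years, time term, trend report or sensitivity analysis for drift is described for H2_c.

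One general sentence in that section could let in further covariates: "sociodemographics or other variables found to significantly influence primary outcomes may be tested for inclusion as statistical controls". It is optional and does not name calendar time. Double-robust estimation is mentioned for the H2_a model, not for H2_c.

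**The concern.** H2_a and H2_b are fitted within the study cohort. H2_c is the only contrast with men who were not offered MoodGym, and the Study Design section relies on it to judge the intervention's impact on program outcomes.

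The control window covers nine calendar years. If all participants enrolled after it closed, treatment and era coincide completely. The four matching variables describe the men, not the period in which they attended, so good balance on them says nothing about drift. With no concurrent arm, drift would not show up elsewhere in the data either. A steady fall in reported risk behaviour would look like benefit on an endpoint comparison, and a steady rise would hide a real benefit. Adding more controls from the same years narrows the interval without moving the biased estimate.

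**Working it through.** **Inputs from the documents**
- Control years: 2009 to 2017 (Statistical Analyses).
- Planned study size: 42 (Table 1, "Enroll 42 MA-Using MSM (6/mo")). Table 1 marks seven enrolment months, and 6 × 7 = 42 reproduces the figure. It is an accrual target; no power calculation is given.
- Outcome model: negative binomial for counts, logistic for a dichotomous outcome.

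**Assumptions, because the documents are silent**
- Cohort year 2018. The reference list carries access dates of March 2018, so enrolment before 2018 is unlikely.
- Matched controls spread evenly over the years in the pool.
- A constant yearly proportional change g in the outcome level, and no MoodGym effect.

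**Mean gap.** Full pool: (1 + 2 + … + 9)/9 = 5 years. Pool of 2015-2017: (1 + 2 + 3)/3 = 2 years.

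**Spurious rate ratio, endpoint contrast.** With the cohort mean set to 1, controls from k years earlier have mean (1+g)^(−k). The apparent ratio is 1 divided by the average of these.

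| Yearly change g | Control average, 2009-2017 | Ratio, 2009-2017 | Control average, 2015-2017 | Ratio, 2015-2017 |
|---|---|---|---|---|
| −2% | 1.108 | 0.90 | 1.041 | 0.96 |
| −3% | 1.168 | 0.86 | 1.063 | 0.94 |
| −5% | 1.304 | 0.77 | 1.109 | 0.90 |
| +3% | 0.865 | 1.16 | 0.943 | 1.06 |
| +5% | 0.790 | 1.27 | 0.908 | 1.10 |

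A 2019 cohort adds a year to the gap. At −5% the ratios become 0.73 (all years) and 0.86 (2015-2017).

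**What this does to a test.** Further assumptions: two-sided 5% Wald test on the log rate ratio, 42 participants against 42 controls, control mean 5, negative binomial dispersion k = 1.
- Standard error at g = −5%, all years: the cohort mean is 5 × 0.767 = 3.83, so SE = √[(1/3.83 + 1)/42 + (1/5 + 1)/42] = 0.242.
- z = ln(0.767)/0.242 = −1.10, so the false-positive rate is about 19.5% against a nominal 5%, nearly all in favour of MoodGym.
- With 2015-2017 controls the rate is about 7.2%.
- The all-years figure is 29.6% for k = 0.5 and 12.9% for k = 2. With three controls per participant and k = 1 it rises to 26.6%.
- Masking: for a true ratio of 0.6 (k = 1), power is 55% with no trend, 32% at +3% and 21% at +5% a year.

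**Dependence on the contrast.** Let the level fall 5% a year while the program always halves the outcome. A cohort going from 10 to 5 is compared with controls going from 13.04 to 6.52.
- Endpoint ratio: 5/6.52 = 0.77, which appears to favour MoodGym.
- Absolute reduction: 5.0 against 6.5, which appears to go against MoodGym.
- Proportional change: 0.50/0.50 = 1.00, no bias.

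The same drift therefore gives three different answers, and the plan does not say which contrast H2_c uses.

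**The case against.** The strongest reply is that H2_c, as worded in the specific aims, concerns reductions, and a contrast of proportional change is unbiased when only the level drifts. That is correct, and it means the bias may be nil. It does not settle the matter, because the Statistical Analyses section contrasts outcomes, states no baseline adjustment for H2_c and does not choose between absolute and proportional change. A proportional contrast would still be biased if the program's own effect had changed over the years.

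A second reply is that the covariate clause could admit entry year. It could, but it commits to nothing. Without overlap in years, a time effect could be estimated only among controls and extrapolated to the cohort, which needs to be planned.

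Third, exact matching on year is impossible, so its absence is no fault in itself. This stands. The gap is the lack of any other handling of era.

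Some stronger readings are tempting but unsupported:
- A reader might infer from the plan's attention to PrEP that uptake was changing over these years and shifting risk behaviour. The documents treat uptake and adherence as individual outcomes of participants and describe no calendar trend.
- A reader might take 6 a month as program intake, so that 2015-2017 would supply 6 × 12 × 3 = 216 candidates, about 5 per participant. Six a month is planned study enrolment; past intake is not given, so the cost in pool size is unknown.
- A reader might suppose that a narrower window was weighed and rejected. No section discusses it.

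**Conclusion.** The concern holds in a limited form. H2_c ignores entry year across a nine-year control window, plans nothing to detect or reduce drift, and leaves open whether its contrast is sensitive to drift. The documents give no evidence that a trend exists, so they do not show that H2_c is biased, only that it is exposed.

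For an endpoint contrast, a 2018 cohort and even sampling over years, falls of 2% to 5% a year would produce ratios of 0.90 to 0.77 from drift alone, reduced to 0.96 to 0.90 with 2015-2017 controls. The error rates rest further on the assumed mean, dispersion and matching ratio. H2_a and H2_b do not use the historical controls and are not affected by this point. It is an inexpensive improvement to a pilot analysis.

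**What to change.** Amend the H2_c text in Statistical Analyses before the control data are matched:

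1. Define H2_c as a baseline-adjusted change contrast, on a stated scale, and bring the wording in the specific aims and the analysis section into line.
2. Report the outcome and its change from baseline by entry year across the 2009-2017 controls, so that any drift in level or in the program's effect can be seen.
3. Run H2_c with controls from the most recent program years that still supply adequate matches, alongside the all-years analysis. The years 2015-2017 are an example, subject to actual program intake. State in advance what counts as agreement, and that a MoodGym effect will be claimed only if the two analyses agree.

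Do not add entry year to the matching variables. If the periods do not overlap, a tight caliper would return no matches, and year in a propensity score would separate the groups completely.

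The cost is SAP wording and one extra run on records the program should already hold. The recent-years analysis has fewer candidate controls, so matches on the other four variables will be somewhat looser. The bias shrinks but does not vanish, because every control would still predate the cohort; the report should say so.
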